4.2 Number of Patients

To assess the feasibility of recruitment and of the protocol procedures (specifically the ≤ 8 hr injury-to-drug timeframe), the study will plan to enroll and treat 10 patients across all study sites.

4.3 Study-related Management (standard-of-care)

The following items will be performed as standard-of-care:

- Vital signs (Temperature, Blood Pressure, Pulse, Respiration Rate, O₂ saturation)
- Blood work; CT scans of the spine and head (as indicated); pre- and post-operative (Day 2) MRI of the cervical spine

Cervical CT studies will reveal the nature of the associated spinal fracture and/or misalignment. Subjects with bilateral cervical facet dislocations or with fracture patterns associated with $> 75\%$ canal compromise will be excluded from the study given that a significant component of their underlying SCI likely involves direct parenchymal and/or ischemic mechanisms [29]. Adherence to acute SCI management guidelines most recently revised by a consensus panel in 2013 [3] will be strongly encouraged. These guidelines include avoidance of hypoxia and hypotension with induced hypertension as needed to keep mean arterial pressure ≥ 85 mmHg for 7 days. Early intervention with surgical decompression and stabilization within 24-48 hrs (when medically feasible) will be encouraged for all patients [30] but will ultimately be left to the discretion of the treating surgeon.

4.4 Study-related management (non-standard of care)

Non-standard-of-care blood work will be obtained at the following time points following the SCI:

- Pharmacokinetic Analysis: Daily, baseline through Day 3
- Biomarkers Levels: Enrollment/Baseline, 24 hours, Day 3, and Day 7

Clinical, imaging, and safety assessments will be performed throughout the study period:

- Patients will be closely monitored clinically for all AEs during the first 28 days of the study. SAEs will be monitored for the entire duration of the study. For the initial hospitalization period, the incidence of AEs will be compared where possible to that of matched controls obtained from the NACTN registry (1:3 ratio with respect to age, co-morbidities, injury level, and injury severity). The 1:3 patient matching will be undertaken by the study statistician.
- Neurological evaluation will be carried out at specific time-points up to one year following SCI to assess for changes in neurological status. The 3, 6, and 12-month ISNCSCI motor/sensory and SCIM vIII scores of the patients will also be compared where possible to that of matched controls from the literature and from the NACTN registry.

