1.0 SYNOPSIS

1.1 Design

This will be a prospective multi-center single arm open-label pilot study of oral glyburide in patients with acute traumatic cervical spinal cord injuries (SCI). The study population consists of subjects with acute traumatic ASIA A, B or C SCI, age 18-80 years, and able to start study drug within 8 hours of injury. The study will enroll and treat up to a maximum of 10 patients who will be matched in a 1:3 ratio with historical controls collected from the North American Clinical Trials Network database.

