3.2 Secondary Objectives

- Pharmacokinetics of glyburide following acute cervical SCI: Plasma concentrations will be serially quantified through day 3 following SCI. Comparisons will be made to reported levels achieved healthy patient cohorts
- Neurologic recovery following SCI: The neurologic status of patients will be assessed using the ASIA Impairment Scale (as assessed by ISNCSCI criteria) and the Spinal Cord Independence Measure (SCIM version III) [22]. The motor and sensory sub scores of the ASIA assessment will be determined on first contact,

every day until Day 4, at 1-2-4-6 weeks, and at 3-6-12 months of follow-up. The SCIM version III will be assessed at 3, 6 and 12 months of follow-up. Comparisons will be made to control subjects (with a 1:3 matching ratio in the NACTN registry matched based on age, co-morbidities, initial injury severity, and injury level.

- Serum biomarker levels: Standard enzyme-linked immunosorbent assay (ELISA) techniques will be used to measure blood levels of neurofilament light chain, neuron-specific enolase, tau, S100b, and glial fibrillary acidic protein levels on admission, at 24 hours and on days 3, and 7 following SCI. Comparisons will be made to (i) matched control serum values of non-treated subjects with acute cervical SCIs [23] and (ii) previously published values observed in non-treated control patients [24-26].
- Spinal cord lesion volumetric analysis: Standard sequences (T1, T2, FLAIR, SWI) at 3T field strength will be used to assess the extent of the hemorrhagic lesion and surrounding edema. Patients will be imaged on the day of admission and on day 2 following injury (standard-of-care studies). Volumetric assessments of lesion size (based on manual outlines) will be performed and compared at the two time-points by the study neuroradiologist to assess for the progression of intrinsic cord signal changes [27].

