7.0 STATISTICAL CONSIDERATIONS

Descriptive statistics will be generated for all variables of interest. Categorical measures will be reported with frequencies and percentages and continuous measures with means and standard deviations. The frequency of AEs will be reported (as captured on the modified NACTN form) and, where possible, will be compared to those of the matched controls (along with corresponding confidence intervals). We will match study patients and the historical NACTN cohort data on criteria including: age, co-morbidities, injury level, and injury severity (ASIA A, B or C SCI). Additionally, the number of patients who were otherwise eligible for the study but did not enroll due to lack of infusion within 6 hours will be reported. Secondarily, matched tests will be utilized to compare neurologic outcomes between those receiving glyburide and matched historical controls.

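### The control comparison of 3-, 6- and 12-month neurologic scores gives no role to the baseline motor and sensory scores that the trial collects

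*Combined protocol and SAP*

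**What the plan says.** Section 4.2 says that "the study will plan to enroll and treat 10 patients across all study sites", and section 1.1 has them "matched in a 1:3 ratio with historical controls collected from the North American Clinical Trials Network database". The full complement is therefore 10 treated patients and 30 controls.

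For the neurologic comparison, section 4.4 states that "The 3, 6, and 12-month ISNCSCI motor/sensory and SCIM vIII scores of the patients" are to be set, where feasible, beside those of matched controls. It draws these "matched controls from the literature and from the NACTN registry". The sentence before it says that the patients' own evaluations are made "to assess for changes in neurological status". Section 7.0 gives the method: "matched tests will be utilized to compare neurologic outcomes between those receiving glyburide and matched historical controls". Section 1.4 says the same in the synopsis. Neither names a model, a covariate or a change score.

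Section 7.0 lists the matching criteria, in a list worded as open-ended, as age, co-morbidities, injury level and injury severity, with severity spelled out as ASIA A, B or C. Section 3.2 gives the same four for the neurologic comparison.

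Baseline scores exist for the trial patients. Section 5.1 includes the ISNCSCI motor and sensory examination at screening, and section 3.2 says that the sub-scores "will be determined on first contact". SCIM is first scheduled at 3 months, so it has no baseline value.

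**The concern.** ASIA grade is a three-level category here, while the outcomes are motor and sensory scores. Two patients matched on grade, level, age and co-morbidities can still start from different scores. If the comparison uses follow-up scores alone, any such starting difference that persists becomes part of the apparent drug effect.

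Two things are at stake. One is precision: an available predictor of the outcome is left out of a comparison with only 10 treated patients. The other is systematic imbalance, which is possible because the controls are historical and not randomised. Section 10.0 expects this study to supply preliminary data on neurologic outcome for the design of a phase II/III trial, so the estimate will be used even though it is not confirmatory.

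**Working it through.** The plan states no SD, correlation, effect size, alpha or power for this comparison, so there is no figure of its own to reproduce. The check asks how much a baseline adjustment could matter.

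**Inputs from the documents.** 10 treated (4.2); ratio 1:3, so 3 × 10 = 30 controls (1.1).

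**Assumptions.** Outcomes are in units of the SD left after matching. ρ is the correlation between baseline and follow-up score that remains after matching, varied from 0 to 0.7. Tests are two-sided at 5%.

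**Step 1, unadjusted standard error.** SE = √(1/10 + 1/30) = √0.1333 = 0.365 SD. The difference detectable with 80% power is (1.960 + 0.842) × 0.365 = 1.02 SD.

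**Step 2, effect of adjustment on precision.** Adjustment multiplies the SE by √(1 − ρ²). Estimating one slope within 10 sets of four costs a further factor of about √(1 + 1/27) = 1.018. A simulation of 20,000 trials with 10 matched sets of 1:3 gave the ratios in the third column. The last column is 1.02 × √(1 − ρ²), without the slope cost.

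| ρ after matching | √(1 − ρ²) | Simulated SE ratio | Detectable difference (SD) |
|---|---|---|---|
| 0 | 1.00 | 1.02 | 1.02 |
| 0.3 | 0.95 | 0.97 | 0.98 |
| 0.5 | 0.87 | 0.88 | 0.89 |
| 0.7 | 0.71 | 0.73 | 0.73 |

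**Step 3, how large an imbalance chance can leave.** If matching leaves only chance differences, the difference in baseline means also has standard deviation 0.365 SD. The probability that it exceeds 0.3 SD in either direction is 2 × [1 − Φ(0.3/0.365)] = 41%. For 0.5 SD it is 2 × [1 − Φ(0.5/0.365)] = 17%.

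**Step 4, what an imbalance does.** The unadjusted difference shifts by ρ × imbalance. For 0.5 SD this is 0.5 × 0.5 = 0.25 SD at ρ = 0.5, and 0.7 × 0.5 = 0.35 SD at ρ = 0.7.

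**Step 5, error rate if that imbalance is systematic.** The shift in SE units is 0.25/0.365 = 0.68 or 0.35/0.365 = 0.96. A nominal 5% test then rejects in 10.5% or 16% of trials with no drug effect. This step does not apply to chance imbalance.

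**Step 6, covariate or change score.** With equal variances, a change score multiplies the SE by √(2(1 − ρ)): 1.18 at ρ = 0.3, 1.00 at 0.5 and 0.77 at 0.7. Below ρ = 0.5 it is less precise than the follow-up score alone. Covariate adjustment is never worse by more than about 2% in this range.

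**The case against.** The strongest reply is that baseline severity is already handled. Matching on grade and level removes part of the imbalance, the matching list is not closed, and section 3.2 speaks of initial injury severity without limiting it to grade. This stands in part. It is why the relevant correlation is the one left after matching, and why the gain may be close to nil. It does not give the motor and sensory scores a role, because no section names them as matching variables.

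A reader might infer that the plan has chosen a raw-score analysis that rejects baseline. The documents do not say that. They name follow-up scores and matched tests and are otherwise silent. The stated purpose of looking at neurologic change would be compatible with a change-based analysis, but it describes the patients' own evaluations and does not define the control comparison.

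A reader might also infer that chance imbalance makes the result biased. It does not do so unconditionally, because chance imbalance is already part of the unadjusted standard error. It is a bias only given the imbalance observed, or if the imbalance is systematic, which is possible with historical controls but not shown.

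It is also fair to say that adjustment is not free. The documents do not confirm that the registry holds baseline motor and sensory scores, or when its examinations were done. Trial patients must start drug within 8 hours of injury, so their baseline examination is early. Adjusting for scores taken at a different time could add bias.

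Finally, a reader might take section 4.4 to plan a formal test against published values. Sections 1.4 and 7.0 tie the matched tests to matched historical controls, so this is a minor point of wording.

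**Conclusion.** The point holds as a better method than the one stated, for a secondary and preliminary comparison. The planned comparison is matched tests on follow-up scores. Baseline severity enters only through matching, and the collected baseline motor and sensory scores have no stated role.

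The gain rests entirely on the assumed correlation after matching: a loss of about 2% in standard error at 0, and reductions of about 3% at 0.3, 12% at 0.5 and 27% at 0.7. The documents do not support a claim that the gain must be large. The shift of 0.25 to 0.35 SD also needs an actual baseline imbalance of 0.5 SD, which is assumed. Nothing here touches the primary feasibility and safety objectives, and adjustment would not remove other differences between trial patients and historical controls.

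**What to change.** In sections 4.4 and 7.0, state the following before outcomes are compared:

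- ISNCSCI motor and sensory scores at 3, 6 and 12 months are compared with registry controls in a model that respects the matched sets (for example, matched set as a random effect) and adjusts for the same score at baseline. The adjusted difference is reported with its 95% confidence interval. Change from baseline may be shown descriptively.
- SCIM has no baseline value, so its comparison adjusts for baseline motor score.
- Literature values are given as descriptive context, without a test.
- The registry extract includes baseline motor and sensory scores and the times of those examinations. The adjustment is made only if these are available and comparably timed. Otherwise the unadjusted matched comparison is reported with that limitation stated.

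This is a cheap improvement. It needs no extra patients, visits or trial assessments. The costs are the additional registry fields and one more model parameter, worth about 2% in standard error if baseline turns out to be uninformative.

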5.0 STUDY ASSESSMENT AND PROCEDURES

5.1 Screening

Patients with suspected acute cervical SCI will be screened upon arrival to hospital. These evaluations will occur prior to enrolment:

- Vital signs (Temperature, Blood Pressure, Respiration rate, Pulse, O₂ saturation, Height, Weight)
 - Note: Height and Weight can be estimated if patient cannot be measured.
- Physical examination and Medical History
- Cervical SCI Time, Cause, and Level of injury
- Demographics and Clinical Variables (age, race, gender, and BMI)
- Neurological examination including ISNCSCI motor and sensory assessments
- ECG (12-lead), read within 12 hours and recorded as clinically significant or non- clinically significant by study team member
- Clinical laboratory tests:
 - Pregnancy test for women of child-bearing potential
 - Hematology: complete blood count
 - Chemistry: electrolytes (sodium, potassium, chloride, bicarbonate), BUN, creatinine, glucose

- Liver Function Tests: AST, ALT, bilirubin (total and direct), and alkaline phosphatase.
 - Glyburide can commence if liver function tests are not yet available but will be discontinued if ALT > 3 times upper limit or bilirubin > 2 times upper limit of normal.

Because pertinent patient information will already be collected as part of the standard of care, and to reduce additional study-specific procedures, screening and baseline information may be taken from the patient's medical records prior to obtaining informed consent. However, informed consent will be obtained prior to performing any study-specific procedures.

Once study eligibility has been confirmed (inclusion/exclusion criteria are met) and informed consent obtained, the patient will be enrolled into the study.

5.2 Registration Procedures

General Guidelines

Primary health care personnel (residents, attending staff, and nurse practitioners) at participating centers will identify potential subjects and will then contact the site coordinator who will then verify eligibility and register the patient using the electronic data capture system (REDCap)

Following registration, patients should begin protocol treatment within 8 hours of the injury. Issues that would cause treatment delays should be discussed with the Study Principal Investigator.

Patients may be registered by a participating site only after the initial IRB approval for the site has been forwarded to the Coordinating Center and the Coordinating Center has activated the site. Eligible patients who consent to participate in the study will be entered on the study by the local site.

5.3 Registration Process

To register a patient, the following documents should be completed and uploaded to the electronic data capture system (REDCap) by the research team:

- Copy of required clinical and radiologic tests
- Signed patient consent form
- HIPAA authorization form
- Eligibility Screening Worksheet
- Registration Form

Eligible patients will be enrolled within the first 8 hours after documented trauma, so that oral glyburide administration can begin no later than 8 hours after injury. This injury-to-drug timeframe appears feasible given the injury-to-admission times reported in recent SCI studies. For instance, in the phase 1/2a Riluzole study [4], the mean injury-to-admission time was 3.0 ± 1.8 hours (median 2.3 hours). The median injury-to-drug time of 8.5 hours in that study likely reflects the time taken for additional MRI studies (in addition to CT imaging).

5.4 On-Study: Baseline

These evaluations occur following subject enrollment, prior to the subject receiving glyburide

- Concomitant medications (including all medications taken within 7 days prior to screening)
- Medical procedures (performed since acute SCI)
- Baseline AEs (beginning at the time of enrollment)
- PK sample (serum)
- Biomarker sample (serum)
- CT and MRI studies
 - CT studies will be performed and reviewed prior to enrollment. Standard of care cervical MRI may be initiated prior to start of study drug but this is not a requirement. Study drug will be administered as soon as possible following enrollment irrespective of whether MRI has been performed.

5.5 Study Drug Description, Dose, and Administration

Enrolled patients will receive 12 doses of glyburide starting within 8 hours of SCI. The dosing regimen involves an initial dose of 1.25 mg followed by eleven consecutive doses of 0.625 mg every 6 hours. The total daily dose of glyburide on Day 1, Day 2 and Day 3 will be 3.125 mg, 2.5 mg, and 2.5 mg respectively (see Table 2).

Table 2: Study Dosing

	Day 1	Day 2	Day 3
Total Dose	3.125 mg	2.5 mg	2.5 mg
	First dose of 1.25 mg then 0.625 mg every 6 hours	0.625 mg every 6 hours	0.625 mg every 6 hours

This injury-to-drug timeframe will apply to patients managed non-operatively as well as to patients undergoing surgery (likely a majority of patients in the trial). Drug administration should not be stopped as the standard of care diagnostic studies and treatment is provided, including if the patient is transferred to the OR for decompression and stabilization. Hard stop rules for glyburide administration are listed below.

In the event a dose of glyburide is missed (beyond 2.5 hours from the expected administration time), the next dose should be administered at 1.25 mg followed by the usual 0.625 mg dose for subsequent administrations. If the missed dose is acknowledged within 2.5 hours of the expected administration time the dose should be given and the deviation noted.

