5.7 Interventions Related to Blood Glucose

- **Insulin**

Insulin is not permitted during the period of study drug administration when BG < 120 mg/dL. "Tight" BG control (80 – 110 mg/dL) is not permitted during the period of study drug administration.

- **Supplemental Fluids**

Supplemental fluids are to be standard of care except that during glyburide administration, D5NS or D10NS must be used instead of NS if necessary to maintain BG above 80 mg/dL. Total fluid volume should be consistent with site clinical practice and the clinical status of the subject.

- **Hypoglycemia treatment**

Any BG of < 70 mg/dL must be promptly treated with a bolus of D50W at a volume (ml) of $(100 - \text{BG in mg/dL}) \times 0.4$ as per Juneja et al. 2009 [31]. If supplemental fluids are NS, D5NS should be started. If supplemental fluids are D5NS, D10NS should be substituted. All BG < 70 mg/dL also should preferably be verified by laboratory testing, but repeat point-of-care tests may be used as well. To avoid false readings, blood for the repeat test must be drawn prior to treatment with D50W or switching supplemental fluids.

- **Glyburide Dose Reduction**

Glyburide dosing must be reduced if subject is being administered D5NS or D10NS and (i) there is one confirmed BG < 55 mg/dL; or (ii) there are three confirmed BG < 70 mg/dL within a 12-hour period. If (i) or (ii) above occurs and the subject is on NS, D5NS or D10NS must first be started. If criteria (i) or (ii) are still met, then glyburide dosing should be adjusted to every 8 hours until three consecutive blood glucose readings of >70 are noted. If appropriate levels of BG are not reached within 8 hours of the first dose reduction, the next dose of glyburide should be skipped as an additional dose reduction. Glyburide dosage must only be adjusted based on verified laboratory or repeat point-of-care test values that are taken 15 minutes or more following the last administration of insulin.

- **Glyburide Discontinuation**

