5.8 Days 1-7 (0-168 hours)

- The first dose of glyburide must be administered within 8 hours of injury and stopped after 72 hours. Hard stop rules for glyburide administration are listed below.
- As per recommended standard-of-care guidelines [3], subjects will be admitted to the intensive care unit following initial diagnostic testing where continuous respiratory, cardiac, and hemodynamic monitoring will be undertaken [32]. Maintenance of normal blood oxygenation and a mean arterial blood pressure of 85-90 mmHg will be emphasized in this monitored setting continuously over the first full 7 days following injury.

- The following assessments will be performed through day 7 following injury (during and after study drug regimen):
 - Safety labs: 24 hours (± 12 hours), 48 hours (± 12 hours) 72 hours (± 12 hours) and 96 hours (± 12 hours).
 - Hematology: complete blood count
 - Chemistry: electrolytes (sodium, potassium, chloride, bicarbonate), BUN, creatinine
 - Liver Function Tests: AST, ALT, bilirubin (total and direct), and alkaline phosphatase
 - Blood glucose (BG) monitoring will be hourly (± 30 minutes) for Hours 1-24, every 2 hours (± 30 minutes) for Hours 25-48 and every 4 hours (± 60 minutes) for Hours 49-88. If BG < 70 mg/dL, BG monitoring is required every 15 (± 10 minutes) minutes until BG ≥ 80 for 3 consecutive readings without exogenous bolus glucose supplementation, then hourly (± 30 minutes) for the next 12 hours and every 2 hours (± 30 minutes) thereafter.
 - Continuous bedside cardiac telemetry monitoring from Hour 0 through Hour 72
 - ECG (12-lead) at 4-6 hours, 24 \pm 6 hours, 48 \pm 6 hours and 60-72 hours (from the start of study drug regimen). The ECGs will be read within 12 hours, recorded as clinically significant or non-clinically significant, and signed off on by study team member.
 - Blood sampling for PK prior to dosing, at 4-6 hr (prior to the second study drug administration), 24 \pm 6 hours, 48 \pm 6 hours and 60-72 hours.
 - PK Samples to be drawn as close as possible to ECGs
 - Start time of drug and time of subsequent dosing. Record reason for any missed doses.
 - Concomitant medications and procedures/therapies
 - Review safety and AEs

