5.11 Study Calendar

Test and Observations	Screening / Enrollment (up to 6 hours prior to treatment)	Day 1	Day 2	Day 3	Day 4	Day 7	Day 14 or D/C	Day 28 (+/- 7 days)	Day 42 (+/- 7 days)	Day 84 (+/- 14 days)	Day 182 (+/- 14 days)	Day 365 (+/- 30 days)
History & Physical	X											

Vital Signs ^a	X												
Consent	X												
Demographic ^b	X												
Operative Data ^f							X						
Length of Stay							X						
Adverse Events ^k	X	X	X	X	X	X	X	X	X	X	X	X	X
Pregnancy Test ^d	X												
SCI (Cervical) ^e	X												
Inclusion/Exclusion	X												
Concomitant Review	X	X	X	X	X	X	X	X					
Procedures	X												
MRI	X		X										
CT	X												
Labs ^c	X	X	X	X	X		X						
ECG(12-lead)	X	X	X	X									
Drug													
Drug Administration ^{i,j}	X	X	X	X									
Serum Biomarkers ^h	X	X		X		X							
Pharmacokinetic ^g	X	X	X	X									
Outcome Measures													
AIS	X	X	X	X	X	X	X	X	X	X	X	X	X
SCIM vIII										X	X	X	

- a. Temperature, blood pressure, pulse, O₂, respiration, BMI, height and weight (can be estimated if patient cannot be measured). Vitals are to be collected at screening (prior to enrolment).
- b. Demographics: age, race, and gender.
- c. Labs: hematology (complete blood count); chemistry (sodium, potassium, chloride, creatinine, electrolytes, bicarbonate, bun); liver function (AST, ALT, bilirubin total, bilirubin direct, and alkaline phosphatase); blood glucose (Blood glucose (BG) monitoring will be hourly (± 30 minutes) for Hours 1-24, every 2 hours (± 30 minutes) for Hours 25-48 and every 4 hours (± 60 minutes) for Hours 49-88. If BG < 70 mg/dL, BG monitoring is required every 15 (± 10 minutes) minutes until BG ≥ 80 for 3 consecutive readings without exogenous bolus glucose supplementation, then hourly (± 30 minutes) for the next 12 hours and every 2 hours (± 30 minutes) thereafter)
- d. Pregnancy test (only complete if woman is of childbearing potential).
- e. SCI (cervical): time, cause, and level of injury.
- f. Optional: only required if patient has surgery.
- g. Blood sampling for PK prior to dosing, at 4-6 hr. (prior to the second dose of glyburide (glyburide), 24±6 hours, 48±6 hours and 60-72 hours. PK samples to be drawn as close as possible to ECGs.
- h. Serum biomarkers: enrollment/baseline, 24 hours, Day 3, and Day 7.
- i. Cannot continue until enrollment liver function test are available and indicate ALT ≤ 3 X upper limit of normal and Bilirubin ≤ 2 X upper limit of normal

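### The missed-dose rule in Section 5.5 has no exception for a dose skipped under Section 5.7 for low glucose; if *skipped* is read as *missed*, the next dose is doubled and the skipped 0.625 mg is given back

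*Combined protocol and SAP*

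**What the plan says.** Section 5.5 sets the regimen as "an initial dose of 1.25 mg followed by eleven consecutive doses of 0.625 mg every 6 hours", 12 doses in all. It then deals with omissions. A dose counts as missed once it is more than 2.5 hours past its expected time, and the same sentence sets the consequence: "In the event a dose of glyburide is missed (beyond 2.5 hours from the expected administration time), the next dose should be administered at 1.25" (the unit is mg). Doses after that one return to 0.625 mg. A dose noticed inside the 2.5-hour window is to be given late and recorded as a deviation. The section does not restrict the rule by the reason for the omission and does not mention Section 5.7.

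Section 5.7 (Glyburide Dose Reduction) has two steps for low glucose. The first lengthens the dosing interval to 8 hours. If glucose has not recovered within 8 hours of that step, "the next dose of glyburide should be skipped as an additional dose reduction". The size of the dose after the skip is not given, and Section 5.5 is not mentioned.

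Section 5.8 tells sites to note dosing times and adds: "Record reason for any missed doses". It has no separate category for a dose withheld because the protocol required it. Neither the footnotes to the study calendar (Section 5.11) nor Section 6.4 supplies an exception.

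**The concern.** The two rules can meet in the same patient, and they pull in opposite directions. A dose omitted under 5.7 will be more than 2.5 hours past its slot when the next one falls due, and that is the only test 5.5 states. Section 5.7 leaves the next dose unstated. Section 5.5 is the only place that gives a dose size after an omission, so a site looking for what to give next will find that sentence.

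The patient concerned is one whose glucose stayed low after the first reduction. A glucose below 55 mg/dL is a named safety outcome in Section 3.1, and a confirmed value is reportable as an SAE under Table 1. The plan allows up to ten centers (Section 2.0) for 10 patients (Section 4.2), so a site may meet this situation once or never and will have no settled practice. If sites read the rule differently, exposure will differ between patients for reasons unrelated to the regimen, in a study whose objectives are safety and pharmacokinetics.

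**Working it through.** **Inputs.** First dose 1.25 mg, maintenance dose 0.625 mg, interval 6 h, 12 doses, missed-dose threshold 2.5 h, dose after a miss 1.25 mg (all Section 5.5). First reduction to an 8 h interval; second reduction is one dose skipped (Section 5.7). Terminal half-life about 10 h in healthy people (Section 2.2), used for illustration only.

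**Step 1: reproduce the plan's figures.** Day 1: 1.25 + 3 × 0.625 = 3.125 mg. Days 2 and 3: 4 × 0.625 = 2.5 mg each. These match Section 5.5: "The total daily dose of glyburide on Day 1, Day 2 and Day 3 will be 3.125 mg, 2.5 mg, and 2.5 mg respectively". Course total: 1.25 + 11 × 0.625 = 8.125 mg.

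**Step 2: does either reduction meet the 5.5 time test?**
- Moving from 6 h to 8 h delays the next dose by 8 − 6 = 2 h. This is under 2.5 h, so the first reduction does not trigger 5.5.
- A skipped dose is a full interval past its slot when the next one is due (8 h on the reduced schedule). This is over 2.5 h, so the second reduction meets the test as worded.

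**Step 3: the two slots.**
- No skip: 0.625 + 0.625 = 1.25 mg.
- Skip, then the 5.5 rule: 0 + 1.25 = 1.25 mg.
- Net change in cumulative dose from the skip: 0 mg. Ratio of the single dose to the usual one: 1.25 / 0.625 = 2.

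**Step 4: a whole course.** Assume the 8 h interval starts after the hour-24 dose and stays in force, and that the hour-32 dose is the one skipped. Doses through hour 24 are 1.25 + 4 × 0.625 = 3.75 mg. The third row only isolates the effect of the skip; it is not a recommendation.

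| Schedule | Dose after hour 24 through hour 48 | Course total |
|---|---|---|
| Planned, every 6 h | 4 × 0.625 = 2.5 mg | 8.125 mg |
| Every 8 h, no skip | 3 × 0.625 = 1.875 mg | 3.75 + 5 × 0.625 = 6.875 mg |
| Every 8 h, skip, next dose counted at 0.625 mg | 2 × 0.625 = 1.25 mg | 3.75 + 4 × 0.625 = 6.25 mg |
| Every 8 h, skip, next dose under 5.5 | 1.25 + 0.625 = 1.875 mg | 3.75 + 1.25 + 3 × 0.625 = 6.875 mg |

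Rows 2 and 4 agree, so the skip is fully offset. Row 4 remains 8.125 − 6.875 = 1.25 mg below the planned course, so the interval change is not undone.

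**Step 5: timing, as an illustration.** Assume one compartment, instant absorption and a 10 h half-life. The amount present is the sum of each dose × 2^(−hours since dose / 10).
- Just before hour 40: about 0.93 mg with no skip and 0.57 mg with the skip. The dose-free gap is real.
- Just after the hour-40 dose: about 1.55 mg with no skip, 1.19 mg with the skip alone, and 1.82 mg with the skip plus the 5.5 rule.
- For comparison, the unreduced 6 h schedule gives about 1.79 mg just after the hour-36 dose and 1.82 mg just after the hour-48 dose.

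Under the literal reading, the amount is therefore briefly higher than if nothing had been skipped, and about equal to the level just after a dose on the unreduced schedule.

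**The case against.** The strongest reply is that 5.5 and 5.7 use different words for different things. *Missed* suggests an accident, while *skipped* is an instruction. The second half of the 5.5 rule supports this: a missed dose noticed within 2.5 hours is to be given and logged as a deviation. If a 5.7 skip counted as missed, that sentence would require the withheld dose to be given, directly against 5.7. It can also be argued that a dose the protocol orders to be left out has no expected administration time. This is good evidence of intent, and it stands as such. It does not put an exception on the page: the only stated test is lateness, and Section 5.8 also uses *missed* without distinguishing withheld doses.

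Three further points stand and limit the concern. Section 6.4 requires the drug to be stopped if the low-glucose criteria are met again after a reduction, so some patients would never reach the dose after a skip. (Section 5.7 allows two reductions before stopping; that difference is a separate matter for reconciliation.) A skip can still occur when glucose has merely failed to recover and the criteria have not recurred. Second, Section 5.7 requires prompt dextrose treatment and Section 5.8 close glucose monitoring in the interval. Third, dosing times and reasons are already recorded, so exposure can largely be reconstructed for pharmacokinetics.

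A reader might also infer that the liver-test hold in the study calendar, "Cannot continue until enrollment liver function test are available", creates the same problem. It does not. If the results exceed the limits, the drug is discontinued (Sections 4.1 and 5.1). If they are acceptable, the reason for the hold has gone. No hypoglycemia reduction is undone in either case.

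**Conclusion.** The concern holds as an unreconciled ambiguity between 5.5 and 5.7. If *skipped* is read as *missed*, the 5.5 rule offsets the whole 0.625 mg removed by the skip and doubles the next single dose, in a patient whose glucose had not recovered within 8 hours of the first reduction. The dose arithmetic needs no assumption beyond that reading. The course totals assume when the 8 h interval starts and that it persists, and the drug-amount figures rest on a deliberately simple model.

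Two stronger readings are tempting and are not supported. One is that the protocol orders a doubled dose after hypoglycemia: it does not say this, and the wording of 5.5 points toward inadvertent omissions. The other is that the safety reduction as a whole is cancelled: the 8 h interval and the dose-free gap both survive, and only the skipped 0.625 mg is at issue.

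The documents give no basis for estimating how often the full sequence would occur. It requires confirmed low glucose on dextrose fluids, a first reduction, no recovery by 8 hours, no discontinuation, and a site that takes the literal reading. The point deserves correction even if the sequence is rare, because a stated dosing rule can work against a hypoglycemia safeguard and the correction is cheap.

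**What to change.** The sponsor should reconcile Sections 5.5 and 5.7. Section 5.5 should state whether its missed-dose rule covers doses withheld under 5.7 or only unplanned omissions, and 5.7 should cross-refer to that statement so that the dose following a skip is no longer left to inference. What that dose is remains a clinical decision for the sponsor; none is proposed here.

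The reason for omission already collected under Section 5.8 should distinguish a missed dose from one withheld per protocol, so that safety and pharmacokinetic summaries can separate the two.

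The cost is one or two sentences in an amendment and one code on the case report form, with no additional patients or procedures.
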